### 10.5 Reporting to FDA

Serious adverse events will be forwarded to FDA by the IND Sponsor (Safety Project Manager IND Office) according to 21 CFR 312.32.

**It is the responsibility of the PI, and the research team, to ensure serious adverse events are reported according to the Code of Federal Regulations, Good Clinical Practices, the protocol guidelines, the sponsor's guidelines, and Institutional Review Board policy.**

### 10.6 Serious Adverse event Reporting to Karyopharm Inc.

All SAEs, whether related or unrelated to selinexor, pregnancies and reports of overdose regardless of suspected causality and expectedness will be reported immediately but not later than 24 hours of the PI becoming aware of the SAE to Karyopharm's SAE Management team who will ensure data is captured in Karyopharm's Pharmacovigilance system. The PI will forward completed SAE and pregnancy forms by email to [[contact]](mailto:[contact]).

Information not available at the time of the initial report (e.g., an end date for the adverse event or laboratory values received after the report) must be documented on a follow-up report. A final report to document resolution of the SAE is required.

## 11.0 STATISTICAL CONSIDERATIONS

The primary objectives of the study are to evaluate safety and efficacy of selinexor in combination with sorafenib in patients with FLT3-ITD and -D835 mutated AML. The total accrual is 52 patients (Phase I: up to 12 patients and Phase II: 20 patients per cohort).

### 11.1 Phase I

In order to determine the MTD of selinexor in combination with sorafenib, we will use the standard 3+3 design for dose finding. The MTD is defined as the highest dose level with  $\leq 1$  out of 6 patients experience a DLT during the first 28 days of treatment. **DLT is defined in section 3.4 (page 13)**. The 3+3-dosing algorithm is presented in section 3.3 and the dosing schema for the combination treatment is shown in Table 3. The RP2D will be selected at the end of the phase I portion based on safety and efficacy of selinexor and sorafenib after discussion with the sponsor and the supporting company (Karyopharm). The Investigator is responsible for completing the cohort summary template prior to advancing subjects to the phase II part. Once RP2D has been established, any patients

still on study at a dose lower than RP2D can be dose escalated up to RP2D in accordance with the dose-escalation guidelines in section 5.2.3.

## 11.2 Phase II

The primary objective of the phase II is to evaluate the efficacy of the combination. The study has two cohorts (maximum of 20 patients for each cohort): (1) FLT3-ITD and –D835 mutated relapsed/refractory AML previously exposed to any FLT3 inhibitor, and (2) FLT3-ITD and –D835 mutated relapsed/refractory AML with no prior exposure to any FLT3 inhibitor.

For all the cohorts, the primary endpoint is the achievement of CRc (CRc=CR/CRp/CRi) at any time during the first three cycles of therapy and toxicity assessed at the end of one cycle of therapy. CRc and toxicity will be monitored simultaneously using the Bayesian approach of Thall, Simon, Estey (1995, 1996) and the extension by Thall and Sung (1998) separately for each cohort. Multic Lean Desktop (version 2.1) was used to generate the stopping boundaries and the OC tables for futility and toxicity monitoring.

- **Cohort #1: Patients with relapse FLT3-ITD and –D835 mutant AML (FLT3 inhibitor naïve cohort):**

The historical data suggested a CRc rate of 20% for this population and the target CRc with selinexor and sorafenib combination is 35%. The treatment will be considered worthy of further investigation if it elicits an increase in CRc to 35% with acceptable toxicity. A >30% therapy related non-hematological grade 3/4 toxicity rate is considered unacceptable. Given this, we will stop enrollment into this cohort if the observed patients' data suggest that:

- 1)  $\Pr(\text{CR}_{cE} > \text{CR}_{cH} + 0.15 | \text{data}) < 0.025$  or
- 2)  $\Pr(\text{TOX}_E > 0.30 | \text{data}) > 0.90$

Here  $\text{CR}_{cE}$  and  $\text{CR}_{cH}$  are the CRc rate for selinexor in combination with sorafenib and the historical treatment, respectively.  $\text{TOX}_E$  is the toxicity rate for selinexor in combination with sorafenib. That is, if at any time during the study we determine that there is a less than 2.5% chance that the average CRc rate improves over historical CRc rate by more than 15% we will stop enrollment to this cohort. The second condition will stop the study early if excessive therapy-related non-hematological grade 3/4 toxicity (>30%) is highly probable (i.e., probability >90.0%) for the CRcE and CRcH are assumed to follow a prior of Beta (0.4, 1.6) and a constant of 20%, respectively. The stopping boundaries for CRc, based on these assumptions and monitoring conditions are found in **Table 6**. We will apply these stopping boundaries continuously starting from the fifth patient in a cohort size of 5 patients. For example, accrual will cease if 0 patients experiences CRc among the first 10 patients treated.

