### 3.0 STUDY DESIGN:

#### 3.1 General

The study will be a phase I/II, single-institution, open-label, non-randomized, parallel group clinical trial. The phase II will include two separate cohorts to be enrolled simultaneously. All patients will be registered through CORE/PDMS.

- **Phase I**
  - This will include FLT3-ITD and –D835 mutated patients with relapsed/refractory AML, including patients who may have been previously exposed to one or more FLT3-inhibitors. Relapsed/refractory status defined by the failure of at least one prior cycle of chemotherapy (including but not limited to cytotoxic chemotherapy, hypomethylator therapy, immune-based therapy, stem cell transplant or stem cell therapy, FLT3-inhibitor therapy, investigational therapy, and others).
  - The DLT assessment period will be performed only during Cycle 1 of Phase I.
  
- **Phase II in two cohorts**
  1. **Cohort 1 (FLT3 inhibitor failure cohort)** in FLT3-ITD and –D835 mutated relapsed/refractory AML who have failed therapy with up to two prior salvage regimens (HSCT or stem cell therapy for patients who previously underwent HSCT/stem cell therapy in remission will not be considered a salvage regimen) and have previously been exposed to at least one prior FLT3 inhibitor.

2. **Cohort 2 (FLT3 inhibitor naive cohort)** in FLT3-ITD and –D835 mutated relapsed/refractory AML who have failed therapy with up to two prior salvage regimens (HSCT or stem cell therapy for patients who previously underwent HSCT/stem cell therapy in remission will not be considered a salvage regimen) with no prior exposure to any FLT3 inhibitor.

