**Table 7. Stopping boundaries for Toxicity**

Stop accrual if the number of drug-related non-hematological grade 3/4 toxicities is greater than or equal to indicated (i.e., # patients with toxicities) among the number of patients evaluated				
# patients evaluated	5	10	15	20
# patients with toxicities	4-5	6-10	8-15	Always stop with this many patients

Multc Lean Desktop (version 2.1.0) was used to generate the toxicity and futility stopping boundaries and the OC table (Table 8). In order to utilize the software for the design, a 20.0% ORR and beta (0.4, 1.6) priors were assumed for the standard treatment response distribution and experimental treatment response prior distribution, respectively. In addition, a 30% toxicity constant rate and beta (0.6, 1.4) priors were assumed for the standard treatment toxicity constant rate and experimental treatment toxicity prior distribution, respectively.

The probability of stopping the study early if the true ORR of the combination treatment was 35% and the true toxicity rate was 30% was 23.8%. Probabilities of stopping early for high true toxicity rates (i.e., 50%) were 63.3% when the true ORR was 35% and 57.5% when true ORR rate was 50%.

Table 8. Operating characteristics for simultaneous monitoring response and toxicity rates for patients treated with combination treatment		
True Toxicity Rate	True ORR	Prob(stop the trial early)
0.10	0.20	0.5391
	0.25	0.3835
	0.35	0.1686
	0.45	0.0642
	0.50	0.0378
0.20	0.20	0.5450
	0.25	0.3913
	0.35	0.1791

Table 8. Operating characteristics for simultaneous monitoring response and toxicity rates for patients treated with combination treatment		
True Toxicity Rate	True ORR	Prob(stop the trial early)
	0.45	0.0760
	0.50	0.0499
0.30	0.20	0.5778
	0.25	0.4352
	0.35	0.2384
	0.45	0.1427
	0.50	0.1185
0.40	0.20	0.6650
	0.25	0.5519
	0.35	0.3957
	0.45	0.3198
	0.50	0.3006
0.50	0.20	0.7965
	0.25	0.7278
	0.35	0.6330
	0.45	0.5869
	0.50	0.5752

- **Cohort #2: Patients with relapsed FLT3-ITD and –D835 mutant AML (FLT3 inhibitor failure cohort)**

The historical data suggested a CRc rate of 10% for this population and the target CRc rate with selinexor ad sorafenib combination is 20%. Given this, we will stop enrollment into this cohort if the observed patients' data suggest that:

- 1)  $\Pr(\text{CR}_{cE} > \text{CR}_{cH} + 0.10 | \text{data}) < 0.025$
- 2)  $\Pr(\text{TOX}_E > 0.30 | \text{data}) > 0.875$

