Here CRcE and CRcH are the CRc rate for selinexor in combination with sorafenib and historical treatment, respectively. TOXE is the toxicity rate for selinexor in combination with sorafenib. That is, if at any time during the study we determine that there is a less than 2.5% chance that the average CRc rate improves over historical rate by more than 10% we will stop enrollment to this cohort. CRcE and CRcH are assumed to follow a prior of Beta (0.2, 1.8) and constant of 10%, respectively. The second condition will stop the study early if excessive therapy-related non-hematological grade 3/4 toxicity (>30%) is highly probable (i.e., probability >95.0%). The stopping boundaries for CRc rate, based on these assumptions and monitoring conditions are found in **Table 9**. We

will apply these stopping boundaries continuously starting from the fifth patient and in cohort size of 5 patients. For example, accrual will cease if no patient experiences CRc among the first 10 patients treated.

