**Table 10. Stopping boundaries for Toxicity**

Stop accrual if the number of drug-related non-hematological grade 3/4 toxicities is greater than or equal to indicated (i.e., # patients with toxicities) among the number of patients evaluated				
# patients evaluated	5	10	15	20
# patients with toxicities	4-5	5-10	7-15	Always stop with this many patients

Multc Lean Desktop (version 2.1.0) was used to generate the toxicity and futility stopping boundaries and the OC table (Table 11). In order to utilize the software for the design, a 10.0% ORR and beta (0.2, 1.8) priors were assumed for the standard treatment response distribution and experimental treatment response prior distribution, respectively. In addition, a 30% toxicity constant rate and beta (0.6, 1.4) priors were assumed for the standard treatment toxicity constant rate and experimental treatment toxicity prior distribution, respectively.

The probability of stopping the study early if the true ORR of the combination treatment was 30% and the true toxicity rate was 20% was 28.2%. Probabilities of stopping early for high true toxicity rates (i.e., 50%) were 77.8% when the true ORR was 20% and 75.8% when true ORR rate was 30%.

**Table 11. Operating characteristics for simultaneous monitoring response and toxicity rates for patients treated with combination treatment**

True Toxicity Rate	True ORR	Prob(stop the trial early)
--------------------	----------	----------------------------

Table 11. Operating characteristics for simultaneous monitoring response and toxicity rates for patients treated with combination treatment		
True Toxicity Rate	True ORR	Prob(stop the trial early)
0.10	0.10	0.3500
	0.15	0.1985
	0.20	0.1092
	0.25	0.0582
	0.30	0.0302
0.20	0.10	0.3756
	0.15	0.2301
	0.20	0.1443
	0.25	0.0953
	0.30	0.0684
0.30	0.10	0.4761
	0.15	0.3540
	0.20	0.2820
	0.25	0.2410
	0.30	0.2184
0.40	0.10	0.6552
	0.15	0.5748
	0.20	0.5274
	0.25	0.5004
	0.30	0.4855
0.50	0.10	0.8381
	0.15	0.8003
	0.20	0.7781
	0.25	0.7654
	0.30	0.7584

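### Section 11.2 restates the failure cohort's toxicity cutoff as 95.0% where the rule and Tables 10 and 11 use 0.875, and describes a per-cohort stop as stopping the study

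*Combined protocol and SAP*

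**What the plan says.** Cohorts are named here rather than numbered, because section 3.1 and section 11.2 number them in opposite order.

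Section 11.2 says that CRc and toxicity are monitored "separately for each cohort". Both cohort rules give the same action, "we will stop enrollment into this cohort if the observed" data satisfy either condition. The toxicity cutoff is 0.90 for the inhibitor-naive cohort and 0.875 for the inhibitor-failure cohort. The latter formula reads "TOX}_E > 0.30 | \text{data}) > 0.875" in the extracted text.

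The explanatory paragraphs put the toxicity condition differently:

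- Naive cohort: "The second condition will stop the study early if excessive therapy-related non-hematological grade 3/4 toxicity (>30%) is highly probable (i.e., probability >90.0" percent).
- Failure cohort: "The second condition will stop the study early if excessive therapy-related non-hematological grade 3/4 toxicity (>30%) is highly probable (i.e., probability >95.0" percent).

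In both paragraphs the futility condition is said to stop enrollment to the cohort. The sentences introducing the operating characteristics also speak of the study: "The probability of stopping the study early if the true ORR of the combination treatment was 35" percent (naive), and "The probability of stopping the study early if the true ORR of the combination treatment was 30" percent (failure). The last column of Tables 8 and 11 refers to stopping the trial.

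**The concern.** There are two inconsistencies in one safety rule.

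**Cutoff.** For the failure cohort the rule says 0.875 and its restatement says 95.0%. These are different rules. If the prose were applied, 5 toxicities in 10 patients or 7 in 15 would not close the cohort, although the rule and Table 10 say that they should.

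**Scope.** The rules close one cohort, while the explanatory text closes the study. Because the same paragraphs say that futility closes the cohort, a reader could take the contrast as deliberate. Section 3.1 says "The phase II will include two separate cohorts to be enrolled simultaneously", so the two readings would lead to different actions on the day a boundary is crossed.

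At stake is whether those running the trial close the right cohort at the right count, and whether the stopping probabilities in Tables 8 and 11 describe the rule they think they are applying.

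**Working it through.** **Inputs (all from section 11.2).** Toxicity prior Beta(0.6, 1.4) and fixed reference rate 30% in both cohorts; looks at 5, 10 and 15 patients, with 20 the maximum. Futility boundaries: Table 6 (naive: 0/5, at most 1/10, at most 2/15) and Table 9 (failure: none at 5, 0/10, 0/15).

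**Step 1: which cutoff gives Table 10?** After x toxicities in n patients the posterior is Beta(0.6 + x, 1.4 + n − x). The probability that the rate exceeds 0.30 is:

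| x/n | Pr(rate > 0.30) |
|---|---|
| 3/5 | 0.8745 |
| 4/5 | 0.9751 |
| 4/10 | 0.7110 |
| 5/10 | 0.8798 |
| 6/10 | 0.9625 |
| 6/15 | 0.7662 |
| 7/15 | 0.8927 |
| 8/15 | 0.9597 |

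- Cutoff 0.875: first crossings at 4/5, 5/10, 7/15. This is Table 10.
- Cutoff 0.95: first crossings at 4/5, 6/10, 8/15. This is not Table 10.
- Cutoff 0.90: first crossings at 4/5, 6/10, 8/15. This is Table 7, the naive cohort, where rule and prose agree.

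Table 10 needs a cutoff of at least 0.8745 (so that 3/5 does not stop) and below 0.8798 (so that 5/10 does). The value 0.875 fits and 0.95 does not.

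**Step 2: reproduce Table 11.** With response and toxicity independent and the cohort judged on its own data, P(stop early) = 1 − P(no futility stop) × P(no toxicity stop).

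At CRc 20% the failure cohort avoids a futility stop if there is at least one CRc in the first 10 patients: 1 − 0.8^10 = 0.8926. An exact recursion over groups of five gives the probability that the toxicity boundary is crossed:

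| True toxicity | Boundary 4/5, 5/10, 7/15 | Boundary 4/5, 6/10, 8/15 |
|---|---|---|
| 30% | 0.1957 | 0.0844 |
| 50% | 0.7514 | 0.5588 |

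With the 0.875 boundary:
- 30%: 1 − 0.8926 × 0.8043 = 0.282 (Table 11: 0.2820).
- 50%: 1 − 0.8926 × 0.2486 = 0.778 (Table 11: 0.7781).

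With the 0.95 boundary:
- 30%: 1 − 0.8926 × 0.9156 = 0.183.
- 50%: 1 − 0.8926 × 0.4412 = 0.606.

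All 25 entries of Table 11 are reproduced to within 0.00005 at 0.875. At 0.95 the entries are off by up to 0.191 (toxicity 40%, CRc 30%: 0.4855 − 0.2941).

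**Step 3: cohort or study?** All 25 entries of Table 8 are also reproduced to within 0.00005 when the naive cohort is judged alone. Now suppose a toxicity crossing in either cohort closed both. Take toxicity 30% in both cohorts, target CRc (35% naive, 20% failure) and equal accrual. Allowing for futility closing a cohort first, the failure cohort closes for toxicity with probability 0.1913 and the naive cohort with 0.0774. Then:

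- Naive: 1 − 0.7616 × (1 − 0.1913) = 0.384, against 0.2384 in Table 8.
- Failure: 1 − 0.7180 × (1 − 0.0774) = 0.338, against 0.2820 in Table 11.

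The printed tables therefore describe per-cohort stopping.

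**The case against.** The strongest reply is that nobody is likely to be misled. The counts are printed in Table 10, and section 11.2 presents that table as the toxicity monitoring rule. To miss 5/10 or 7/15, staff would have to set aside both the table and the formula and rebuild a boundary from a parenthesis. The word study is used loosely throughout the section, including for single-cohort probabilities and in the table column heads. The statement that monitoring is separate, the two rules and the table instructions to stop accrual all point to the cohort. This stands as an argument about likelihood and keeps the matter small. It does not remove the contradiction: a safety cutoff is stated with two values, and one is wrong.

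A reader might infer two stronger things, and the documents support neither.

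- *That a toxicity crossing in one cohort is meant to close the whole trial.* The rules, the separate-monitoring statement and all 50 entries of Tables 8 and 11 say otherwise.
- *That per-cohort stopping leaves the other cohort unprotected, so a mandatory pause is needed.* Separate monitoring is an explicit choice and the other cohort keeps its own toxicity boundary. Section 9.2 lets the principal investigator and the IND Office suspend enrollment for toxicity, and section 10.4 sends all serious adverse events to the IND Office regardless of attribution. If true toxicity were 50% in both cohorts at target CRc, one would close for toxicity while the other filled to 20 with probability 0.510 × 0.222 + 0.738 × 0.367 = 0.384. That figure assumes that section 9.2 is never used, and it includes cases where the other cohort is already full. It is an upper limit for inaction and does not show an error in the plan.

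**Conclusion.** The point holds as an error in the text. The 95.0% in the failure cohort's explanatory paragraph contradicts the 0.875 rule, and the tables show that 0.875 is the value used. If the prose were followed, early stopping at CRc 20% would drop by 0.172 (0.778 to 0.606) at 50% toxicity and by 0.099 (0.282 to 0.183) at 30%. These are the consequences of applying the wrong cutoff; they do not describe the trial as its tables would run it. They rest on the stated prior, looks at 5, 10 and 15, and independence of response and toxicity, which together also reproduce the printed tables.

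The study wording is a lesser defect. Per-cohort stopping is clearly the intended reading, and only the prose needs to be brought into line. In the naive cohort the cutoff is consistent at 0.90.

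Whether a crossing in one cohort should prompt any step in the other is a design trade-off that the plan may settle as it has.

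**What to change.** In section 11.2:

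1. In the failure cohort's explanatory paragraph, change 95.0% to 87.5%.
2. In the explanatory paragraphs of both cohorts, say that the toxicity condition stops enrollment to this cohort, as the futility sentence already does.
3. Use the same cohort wording in the sentences that introduce the results of Tables 8 and 11, and in those tables' headings.

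Keep every boundary and every entry of Tables 6 to 11. The cost is a few words in one amendment, with no new patients, data or simulations.

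Optional: state that a toxicity crossing in one cohort is notified to the principal investigator and the IND Office, so that they can decide whether to act under section 9.2. This changes no operating characteristic of the cohort rules. A compulsory pause of the other cohort is not recommended.

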**Table 6. Stopping boundaries for CRc rate**

Stop accrual if the number with overall response is less than or equal to indicated (i.e., #
--

patients with overall response) among the number of patients evaluated				
Number of patients evaluated for CRc	5	10	15	20
Number of patients with CRc (i.e., CR, CRp, or CRi) is less than or equal to	0	0-1	0-2	Always stop with this many patients

The monitoring rule for the toxicity rate, based on these assumptions and monitoring conditions above is found in **Table 7**. For example, accrual will cease if 4 or more patients experience toxicities among the first 5 patients.

**Table 7. Stopping boundaries for Toxicity**

Stop accrual if the number of drug-related non-hematological grade 3/4 toxicities is greater than or equal to indicated (i.e., # patients with toxicities) among the number of patients evaluated				
# patients evaluated	5	10	15	20
# patients with toxicities	4-5	6-10	8-15	Always stop with this many patients

Multc Lean Desktop (version 2.1.0) was used to generate the toxicity and futility stopping boundaries and the OC table (Table 8). In order to utilize the software for the design, a 20.0% ORR and beta (0.4, 1.6) priors were assumed for the standard treatment response distribution and experimental treatment response prior distribution, respectively. In addition, a 30% toxicity constant rate and beta (0.6, 1.4) priors were assumed for the standard treatment toxicity constant rate and experimental treatment toxicity prior distribution, respectively.

The probability of stopping the study early if the true ORR of the combination treatment was 35% and the true toxicity rate was 30% was 23.8%. Probabilities of stopping early for high true toxicity rates (i.e., 50%) were 63.3% when the true ORR was 35% and 57.5% when true ORR rate was 50%.

Table 8. Operating characteristics for simultaneous monitoring response and toxicity rates for patients treated with combination treatment		
True Toxicity Rate	True ORR	Prob(stop the trial early)
0.10	0.20	0.5391
	0.25	0.3835
	0.35	0.1686
	0.45	0.0642
	0.50	0.0378
0.20	0.20	0.5450
	0.25	0.3913
	0.35	0.1791

Table 8. Operating characteristics for simultaneous monitoring response and toxicity rates for patients treated with combination treatment		
True Toxicity Rate	True ORR	Prob(stop the trial early)
	0.45	0.0760
	0.50	0.0499
0.30	0.20	0.5778
	0.25	0.4352
	0.35	0.2384
	0.45	0.1427
	0.50	0.1185
0.40	0.20	0.6650
	0.25	0.5519
	0.35	0.3957
	0.45	0.3198
	0.50	0.3006
0.50	0.20	0.7965
	0.25	0.7278
	0.35	0.6330
	0.45	0.5869
	0.50	0.5752

- **Cohort #2: Patients with relapsed FLT3-ITD and –D835 mutant AML (FLT3 inhibitor failure cohort)**

The historical data suggested a CRc rate of 10% for this population and the target CRc rate with selinexor ad sorafenib combination is 20%. Given this, we will stop enrollment into this cohort if the observed patients' data suggest that:

- 1)  $\Pr(\text{CR}_{cE} > \text{CR}_{cH} + 0.10 | \text{data}) < 0.025$
- 2)  $\Pr(\text{TOX}_E > 0.30 | \text{data}) > 0.875$

Here CRcE and CRcH are the CRc rate for selinexor in combination with sorafenib and historical treatment, respectively. TOXE is the toxicity rate for selinexor in combination with sorafenib. That is, if at any time during the study we determine that there is a less than 2.5% chance that the average CRc rate improves over historical rate by more than 10% we will stop enrollment to this cohort. CRcE and CRcH are assumed to follow a prior of Beta (0.2, 1.8) and constant of 10%, respectively. The second condition will stop the study early if excessive therapy-related non-hematological grade 3/4 toxicity (>30%) is highly probable (i.e., probability >95.0%). The stopping boundaries for CRc rate, based on these assumptions and monitoring conditions are found in **Table 9**. We

will apply these stopping boundaries continuously starting from the fifth patient and in cohort size of 5 patients. For example, accrual will cease if no patient experiences CRc among the first 10 patients treated.

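### Section 11.2 gives two toxicity cut-offs (0.875 and 95%) for stopping accrual in cohort #2, and attaches the 28.2% early-stop probability to the wrong pair of true rates

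*Combined protocol and SAP*

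**What the plan says.** All of this is in section 11.2, under cohort #2, which that section labels the FLT3 inhibitor failure cohort. (Sections 3.1 and 4.1.3 number the two cohorts the other way round; that is a separate matter.)

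- **Formula.** Condition 2 stops enrolment if Pr(TOX_E > 0.30 | data) > 0.875.
- **Prose.** The next paragraph restates that condition, for the same cohort and the same 30% limit, as "toxicity (>30%) is highly probable (i.e., probability >95.0" per cent.
- **Count limits.** Table 10 closes accrual at 4 or more of 5, 5 or more of 10, and 7 or more of 15 patients with toxicity.
- **Prior.** Below Table 10: "a 30% toxicity constant rate and beta (0.6, 1.4) priors were assumed".
- **Futility rule.** The complete response rates for the combination and the historical treatment "are assumed to follow a prior of Beta (0.2, 1.8) and constant of 10%, respectively". Accrual stops if there is a "less than 2.5% chance that the average CR c rate improves over historical rate by more than 10" per cent.
- **Operating characteristics.** The early-stop probability when the "true ORR of the combination treatment was 30% and the true toxicity rate was 20% was 28.2" per cent. The next sentence reads: "Probabilities of stopping early for high true toxicity rates (i.e., 50%) were 77.8% when the true ORR was 20% and 75.8" per cent when it was 30%.

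Table 11 shows 0.2820, in bold, in the row for true toxicity 0.30 and true ORR 0.20. Its entry for true toxicity 0.20 and true ORR 0.30 is 0.0684.

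**The concern.** The cut-off decides when accrual closes for toxicity in a cohort of at most 20 patients, and the plan gives two values for it without saying which governs. In cohort #1 the formula and the prose both say 0.90, so the mismatch is not a drafting convention. The only worked toxicity example for cohort #2, 4 of the first 5 patients, stops under either value and cannot alert a reader. If the two values imply different counts at later looks, someone working from the prose would keep enrolling where Table 10 closes accrual, and Table 11 would not describe the rule in use.

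The 28.2% sentence raises a smaller question. It gives early stopping for a favourable case (response above the 20% target, toxicity below the 30% limit), yet its value is about four times the Table 11 entry for that case (28.2 / 6.84 = 4.1).

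**Working it through.** **Inputs (section 11.2, cohort #2).** Toxicity prior Beta(0.6, 1.4), limit 0.30, cut-off 0.875 or 0.95. Response prior Beta(0.2, 1.8), threshold 0.10 + 0.10 = 0.20, futility cut-off 0.025. Looks at 5, 10 and 15 patients, maximum 20. Response and toxicity are taken as independent.

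**Step 1: toxicity limits.** After x toxicities in n patients the posterior is Beta(0.6 + x, 1.4 + n − x). The probability that the rate exceeds 0.30 is:

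| n | x: probability | x: probability | x: probability |
|---|---|---|---|
| 5 | 3: 0.8745 | 4: 0.9751 | |
| 10 | 4: 0.7110 | 5: 0.8798 | 6: 0.9625 |
| 15 | 6: 0.7662 | 7: 0.8927 | 8: 0.9597 |

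- Cut-off 0.875 gives 4/5, 5/10, 7/15, which is Table 10.
- Cut-off 0.95 gives 4/5, 6/10, 8/15, the same counts as cohort #1's Table 7.
- Table 10 requires that 3/5 does not stop (cut-off at least 0.8745) and that 5/10 does (cut-off below 0.8798). Only a cut-off in that narrow range fits.

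Before the maximum of 20, the two rules part only at exactly 5 of 10 and exactly 7 of 15.

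**Step 2: futility limits.** Pr(response rate > 0.20) is 0.0279 at 0/5 (no stop), 0.0065 at 0/10 and 0.0017 at 0/15 (stop), and 0.0423 at 1/15 (no stop). This reproduces Table 9.

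**Step 3: Table 11.** Early stop = 1 − P(no toxicity stop) × P(no futility stop), from exact binomial sums over the three looks. A patient group with at least one response by 10 cannot stop for futility at 15, so P(no futility stop) = 1 − (1 − ORR)^10. That is 1 − 0.8^10 = 0.8926 at ORR 20% and 1 − 0.7^10 = 0.9718 at ORR 30%.

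At the Table 10 limits, P(no toxicity stop) is 0.8043 at 30% toxicity and 0.9587 at 20%. So:

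- ORR 20%, toxicity 30%: 1 − 0.8043 × 0.8926 = 0.282. Table 11 has 0.2820.
- ORR 30%, toxicity 20%: 1 − 0.9587 × 0.9718 = 0.068. Table 11 has 0.0684.

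All 25 cells agree to within 0.00005 at 0.875. With the 0.95 limits none of the 25 agrees.

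**Step 4: effect of using 95% in place of 0.875.** The last two columns are at ORR 20%.

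| True toxicity | Toxicity stop, 0.875 v 0.95 | Any early stop, 0.875 v 0.95 | Expected enrolment, 0.875 v 0.95 |
|---|---|---|---|
| 10% | 0.2% v 0.1% | 10.9% v 10.8% | 18.9 v 18.9 |
| 20% | 4.1% v 1.3% | 14.4% v 11.9% | 18.6 v 18.8 |
| 30% | 19.6% v 8.4% | 28.2% v 18.3% | 17.2 v 18.1 |
| 40% | 47.1% v 27.4% | 52.7% v 35.2% | 14.7 v 16.4 |
| 50% | 75.1% v 55.9% | 77.8% v 60.6% | 11.8 v 13.7 |

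At ORR 30% and toxicity 50%, any early stop is 75.8% v 57.1%.

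**Step 5: the 28.2% sentence.** The figure is right for ORR 20% and toxicity 30%; the sentence names the two rates the other way round. The matching cohort #1 sentence (ORR 35%, toxicity 30%, 23.8%) pairs the target response rate with toxicity at its limit and agrees with Table 8. The cohort #2 target, where the "rate with selinexor ad sorafenib combination is 20" per cent, fits the same pattern once the rates are exchanged. The 77.8% and 75.8% figures agree with Table 11 as written.

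**The case against.** The best reply is that the operative rule is given as counts. The text refers the reader to Table 10 for toxicity monitoring, and its entries are explicit. The formula, Table 10, every cell of Table 11 and the quoted 77.8% and 75.8% all agree on 0.875; a single parenthetical differs. Harm would require someone to set the table aside and recompute from that parenthetical. Even then expected enrolment changes by fewer than 2 patients, and at true toxicity of 10% to 20% early stopping at ORR 20% moves by at most 2.5 percentage points. The 28.2% slip is editorial, with the correct cell in bold in Table 11.

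Most of this stands. The tables are correct, a team using only Table 10 would apply one consistent rule, and the 28.2% sentence changes no decision. The Step 4 differences are the cost of following the prose, not errors in the tabulated characteristics. What the reply does not remove is that a safety cut-off is stated at two values and nothing says which prevails. The prose version is less protective at two of the three looks, and the gap is widest at high toxicity, where the rule is needed. Agreement among the tables shows what was computed; it cannot settle what was intended.

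**Conclusion.** Both points hold, and the text is wrong as written.

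The 95% in the prose contradicts the 0.875 in the formula and cannot produce Table 10 or Table 11. Following it would lower the chance of a toxicity stop by 11 to 20 percentage points at true toxicity of 30% to 50%. The 28.2% sentence states an operating characteristic about four times the plan's own value for the pair it names, without altering any rule.

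The first point must be fixed because it concerns the rule for closing accrual on safety grounds; the second is a text correction to make at the same time. The figures rest on the stated priors, looks at 5, 10 and 15 patients, and independence of response and toxicity. Exact reproduction of all 25 Table 11 cells supports those assumptions.

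**What to change.** The sponsor should confirm the intended cohort #2 toxicity cut-off, and section 11.2 should then state one value throughout.

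- **If 0.875 stands:** change the 95.0% in the prose to match the formula. Tables 10 and 11 stay as they are.
- **If 95% was intended:** change the formula and regenerate Table 10, Table 11 and the three quoted probabilities. On the calculation above, 28.2%, 77.8% and 75.8% would become 18.3%, 60.6% and 57.1%.
- **In either case:** reword the sentence under Table 10 so that it names a true ORR of 20% and a true toxicity rate of 30%, with the matching table value.

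The cost is two text corrections in the first case, and one software rerun plus the replaced tables and figures in the second.
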